## 12.4 Stopping Rules

To protect the safety of patients, the study incorporates the following stopping rules:

1. If the lower bound of a 1-sided 80% exact binomial confidence interval of death that are probably or definitely attributable to anakinra treatment is  $> 3\%$ . Operationally, any of the following would trigger such a rule: 1 death out of the first  $\leq 7$  patients or 2 death out of the first  $\leq 15$  patients that are probably or definitely attributable to anakinra treatment. If the true probability of death is 1%, the probability of study suspension under the above rule is approximately 0.08; if the true probability is 15%, the probability of suspension is approximately 0.93 (probabilities estimated from 5,000 simulations).
2. If the upper bound of a 2-sided 95% exact binomial confidence interval of responses (ORR) is  $< 75\%$  with 15 subjects at the interim analysis. Operationally, if there are 7 or fewer responses (ORR) among the first 15 subjects, the study will be stopped. Otherwise, the study will continue until 25 subjects are enrolled. If the true probability of ORR is 40%, the probability of stopping under the above rule is approximately 80%; if the true probability of ORR is 80%, the probability of stopping is approximately 0.5% (probabilities estimated from 5,000 simulations).

When a stopping rule is triggered, further enrollment will be suspended pending review by the study Steering Committee (as discussed in section 13.1).

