
In the pivotal clinical trial ZUMA-1, investigating the use of axi-cel in patients with relapsed or refractory LBCL, higher IL-1R antagonist peak serum concentrations were associated with CRS and ICANS severity.

An interim analysis of the first 15 patients treated on this protocol with subcutaneous (SC) anakinra, all patients received all doses of anakinra as planned, without dose adjustments or interruptions, and there were no adverse events (AEs) attributed to anakinra. The rates of any grade CRS and ICANS were 53% ( $\geq$  grade 3: n = 1) and 20% (all  $\geq$  grade 3), respectively, which are lower than those in patients treated at our institution who received liso-cel without prophylactic anakinra (CRS: 68%; ICANS: 27%). We also observed faster resolution of inflammatory biomarkers, such as temperature, CRP, and IL-6. Day+28 complete and overall response rates were comparable in the two cohorts (complete response rate: 33% in anakinra cohort vs. 45% in no-anakinra cohort; overall response rate: 75% in anakinra cohort vs. 85% in no-anakinra cohort).

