## 2.4 Rationale for anakinra dosing, administration route, treatment duration, up-titration

### *Dosing*

We hypothesize the low RA flat dose of 100 mg/day may not be sufficient to mitigate ICANS after CD19 CAR T-cell therapy. Anakinra is a large 17kD-molecule with low permeation into the CSF; high doses of anakinra are needed to achieve neuroprotective concentrations in rhesus monkey models of NOMID, and in humans developing subarachnoid hemorrhage. NOMID, which is characterized by chronic aseptic meningitis, typically respond to higher doses of anakinra (1-8 mg/kg/day). As described above, higher anakinra doses (5-8 mg/kg/day) have been used safely and successfully to treat CAR T-cell related CRS with HLH features. Very high doses of anakinra were also shown to be safe in patients with sepsis (1-2 mg/kg/h intravenously (IV), acute GVHD (up to 3200 mg/day IV), stroke (2 mg/kg/h IV), and subarachnoid hemorrhage (100-500 mg bolus, then 2-10 mg/kg/h IV). In healthy human subjects anakinra doses up to 10 mg/kg IV are not associated with clinical symptoms, and the authors did not report impairment of in vitro T cell proliferation.

Pharmacokinetic studies in healthy adults across a spectrum of body weights have demonstrated that the maximum plasma concentration of anakinra ( $C_{max}$ ) is up to 30-fold higher with IV administration compared to SC administration (~20,000-30,000 ng/mL vs. ~600-1,000 ng/mL). In addition, the area under the concentration-time curve (AUC) was also higher in patients receiving IV anakinra (~10,000-15,000 ng-hour/mL vs. ~8,000-13,000 ng-hour/mL). No new safety concerns were observed.

Therefore, we hypothesize that the IV route will improve the efficacy of anakinra to prevent CRS and ICANS. Anakinra 200 mg will be diluted in 200 mL of sodium chloride 0.9% and administered over approximately 10-30 minutes once daily (prophylactic dose), which can be practically administered in the outpatient setting. Given the encouraging safety data and response rates in patients who received SC anakinra, we do not anticipate significant AEs or impact on CAR T-cell efficacy associated with IV administration.

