## 12.3 Data Analysis

We will perform a first analysis when the number of enrolled patients reaches 15. The posterior probabilities of the absence of any grade CRS will be computed as described above. In our case, we will conclude that the primary endpoint is not reached if no CRS is observed in  $\leq 9$  patients in the first 15 patients treated. Since this is a pilot study, the decision to include the additional 10 patients might be considered based on both the primary and secondary endpoints.

If the total number of patients reaches the maximum sample size of 25, we will reject the null hypothesis and conclude that the primary endpoint is met if the number of patients without CRS is greater than 18 (19 or more patients with no evidence of any grade CRS); otherwise we conclude that the primary endpoint is not met.

**February 2023 update:** although our interim analysis did not meet the primary endpoint, anakinra prophylaxis was feasible, safe, and associated with low rates of mild CRS (8/15; 53%) and ICANS (3/15; 20%). Longitudinal analyses of the participants' temperature and CRP data suggested faster resolution of systemic inflammation compared to patient receiving liso-cel alone. Therefore, we will plan to treat 10 additional patients with the following protocol modification: change from SC to IV administration route, up-titration of the anakinra dose in case of breakthrough CRS or ICANS.

Statistical analysis will include descriptive statistics for which categorical variables will be summarized by number and percentage, and continuous variables will be summarized by median, standard deviation, and range. For binary endpoints, such as the proportion of patient without any grade CRS and the overall response rate (ORR), an exact 95% confidence interval using a binomial distribution will be provided. Time-to-event data will be analyzed using Kaplan-Meier method and the results will be summarized by the median with a 95% CI if appropriate.

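### The anakinra-death rule in 12.4 is one count with no restart, so after 15 SC patients with no attributable event a first attributable death on the IV/up-titration regimen cannot trigger it, even with the count run to 25

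*Combined protocol and SAP*

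**What the plan says.** Section 12.4 has one toxicity stopping rule. It applies "If the lower bound of a 1-sided 80% exact binomial confidence interval of death that are probably or definitely attributable to anakinra treatment is" above 3%. The operational form reads "Operationally, any of the following would trigger such a rule: 1 death out of the first" 7 or fewer patients, or 2 deaths out of the first 15 or fewer. The stated performance is that, at a true death rate of 1%, "the probability of study suspension under the above rule is approximately 0.08", and "if the true probability is 15%, the probability of suspension is approximately 0.93". A trigger suspends enrolment pending Steering Committee review. The second rule in 12.4 concerns response rate, not toxicity; unless it stops the study, "Otherwise, the study will continue until 25 subjects are enrolled".

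The synopsis gives the first 15 patients SC anakinra 200 mg/day and the 10 expansion patients IV anakinra at the same daily dose. Section 12.3 lists the changes for these 10 as "change from SC to IV administration route, up-titration of the anakinra dose in case of breakthrough CRS or ICANS". It does not mention the death rule. For the first 15, Section 2.3.2 reports that "there were no adverse events (AEs) attributed to anakinra".

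**The concern.** The rule is most sensitive at the start: one attributable death among the first 7 patients is enough. After that, two are needed. That early sensitivity was used on the SC regimen. The IV cohort enters with 15 event-free patients already in the denominator, and those patients received a different route and were not treated under the step-up scheme.

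On prophylaxis the peak concentration differs: Section 2.4 puts Cmax "up to 30-fold higher with IV administration compared to SC administration". In patients who are up-titrated the dose itself differs, to 8 mg/kg/day and then 1 mg/kg/h (24 mg/kg/day). The full step 1 dose exceeds 200 mg/day for anyone above 25 kg (200/8). Up-titration may be common. CRS occurred in 8 of the first 15, so at the same rate about 5 of 10 IV patients (10 × 8/15 = 5.3) would qualify for step 1.

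At stake is whether the one formal toxicity rule can react to a first attributable death on the modified regimen, and whether the stated 0.93 tells a reader anything about these 10 patients.

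**Working it through.** **Inputs.** From 12.4: one-sided 80% exact interval, 3% limit, stated probabilities 0.08 and 0.93. From the synopsis and 12.3: 15 SC patients, 10 IV patients, maximum 25. From 2.3.2: no attributable adverse event, hence 0 attributable deaths, in the first 15.

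**1. The printed triggers.** The exact lower bound for x deaths in n is the 20% quantile of Beta(x, n − x + 1). For x = 1 this is 1 − 0.8^(1/n).
- 1/7 gives 3.14% and 1/8 gives 2.75%. One death triggers up to n = 7, as printed.
- 2/15 gives 5.5%, 2/25 gives 3.3%, and two deaths stay above 3% up to n = 27. The criterion itself therefore covers two deaths at any point up to patient 25.

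**2. The stated probabilities.** With monitoring after every patient and total N, P(suspend) = 1 − (1−p)^7 + (1−p)^7 × P(Bin(N−7, p) ≥ 2).

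| N | p = 1% | p = 15% |
|---|---|---|
| 25 | 0.081 | 0.928 |
| 15 | 0.070 | 0.789 |
| Stated | 0.08 | 0.93 |

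The plan's 0.93 reproduces with one continuous count to 25 and not with 15. At p = 15%, the first-7 trigger alone supplies 1 − 0.85^7 = 0.68 of it.

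**3. A first attributable death in the IV cohort.** After 0/15 it falls at n = 16 to 25.
- 1/16: 1 − 0.8^(1/16) = 1.38%.
- 1/25: 1 − 0.8^(1/25) = 0.89%.

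Both are below 3%, as is every value between them.

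**4. Probability of suspension during the 10 IV patients.**
- Single count to 25 after 0/15: two deaths are needed, so P(Bin(10, p) ≥ 2). At 15%: 1 − 0.85^10 − 10 × 0.15 × 0.85^9 = 0.456.
- Same criterion counted from IV patient 1: one death in the first 7, or two by patient 10 (2/10 has a lower bound of 8.33%). P = 1 − (1−p)^7 + (1−p)^7 × P(Bin(3, p) ≥ 2). At 15%: 0.679 + 0.321 × 0.061 = 0.699.

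| True rate | Single count to 25 | IV cohort counted separately |
|---|---|---|
| 1% | 0.004 | 0.068 |
| 5% | 0.086 | 0.307 |
| 10% | 0.264 | 0.535 |
| 15% | 0.456 | 0.699 |

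**5. Cost at a true 1% rate.** From now on, the chance of suspension goes from 0.004 to 0.068. Over the whole trial under the single count it is 0.081. With the rule applied to the first 15, a separate IV count and the single count kept alongside:
- Suspension in the first 15 or on the IV count: 1 − (1 − 0.0704)(1 − 0.0682) = 0.134.
- Extra from the single count: one death among patients 8 to 15 (0.99^7 × 8 × 0.01 × 0.99^7 = 0.0695), then a lone death among IV patients 8 to 10 (0.99^7 × 3 × 0.01 × 0.99^2 = 0.0274). The product is 0.002.
- Total: about 0.136.

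**The case against.** **Part of the loss belongs to any single count.** On one unchanged regimen, a first death at patients 8 to 25 would not trigger either. Whether a modified regimen restarts the count is a design judgement, and 12.4 never uses the word pooled. This stands as a matter of wording, but the reference to the first patients, the absence of any restart and the reproduced 0.93 all indicate one sequence of 25.

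**The exposure contrast can be overdrawn.** A reader might infer from the Cmax figure that the IV cohort as a whole is far more heavily exposed. Section 2.4 does not support that. At the 200 mg/day prophylactic dose its AUC ranges overlap (about 10,000–15,000 IV against 8,000–13,000 SC ng-hour/mL), it reports no new safety concerns, and it cites higher IV doses as safe in other conditions. The larger exposure difference arises in patients who are up-titrated. The regimen is new to this trial, not to all clinical use.

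**Other oversight exists.** Section 13.2 has serious events reviewed as they occur and at least monthly team review of adverse events and stopping rules. Section 13.1 adds DSMC, DSMB and IRB review, and Section 15.0 lets the PI, IRB or FDA terminate the study. So it would be wrong to infer that a first IV death would go unreviewed. None of these sections, however, prescribes an automatic pause after one such death; the DSMB charter is not in the documents.

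**The restart costs more than it first appears.** The new 0.07 at a 1% rate resembles the stated 0.08, and a reader might call them equivalent. They are not: 0.08 covers 25 patients and 0.07 covers 10. The like-for-like changes are those in step 5 of the working.

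**Conclusion.** The point holds for the formal rule. After 0/15, no first attributable death among the 10 IV patients can meet the 3% criterion, and the one-death early trigger is unavailable to the new regimen. The stated 0.93 is correct for one count over 25 patients from the start; it does not describe the protection of the expansion patients. For them the chance of suspension at a 15% rate is 0.46, against 0.70 with a separate count; at 5% it is 0.09 against 0.31.

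This rests on three assumptions: the rule is one sequence; no death in the first 15 was attributed to anakinra, as 2.3.2 implies; and patients are independent with a constant rate within the IV cohort.

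A reader might go further and infer from the printed limit of 15 patients that the rule gives the IV cohort no protection at all. The plan's own figures do not support this: the governing criterion is the lower bound, two deaths meet it up to patient 25, and 0.93 requires the count to run that far. The mismatch between printed limit and criterion needs reconciling as a separate matter. What is missing here is the automatic pause after a first death, not review of the death. The change should be made, as a modest improvement to monitoring.

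**What to change.** In 12.4, apply the existing criterion (80% lower bound above 3%) separately to the IV/up-titration cohort, counted from its first patient. This gives triggers of one attributable death in the first 7 or fewer IV patients, or two within the 10. State the suspension probabilities for n = 10: about 0.07, 0.31, 0.54 and 0.70 at true rates of 1%, 5%, 10% and 15%. Given 0/15, keeping the single count alongside adds nothing, because any two deaths among the 10 already trigger the separate count.

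The drafting cost is one paragraph. The operating cost should be stated with it: at a true 1% rate, the chance of a temporary suspension rises from 0.004 to 0.068 from now on, or from 0.081 to about 0.136 over the whole trial. A trigger leads to a pause for Steering Committee review, not to termination.

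### Safety stopping rule 1: the two-death count ends at patient 15, but the rule's own 80% bound and its quoted 0.93 both need it to run to patient 25

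*Combined protocol and SAP*

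**What the plan says.** Section 12.4 (Stopping Rules), rule 1, has three parts.

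- **Criterion.** "If the lower bound of a 1-sided 80% exact binomial confidence interval of death that are probably or definitely attributable to anakinra treatment is" above 3%. No sample-size limit is attached.
- **Operational counts.** One death in the first 7 or fewer "patients or 2 death out of the first" 15 or fewer. No count is listed beyond patient 15.
- **Operating characteristics.** At a true death rate of 1%, "the probability of study suspension under the above rule is approximately 0.08"; and "if the true probability is 15%, the probability of suspension is approximately 0.93 (probabilities estimated from 5,000 simulations").

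Rule 2, on overall response, is built differently. Its criterion carries its own limit, "with 15 subjects at the interim analysis", and its count follows: "Operationally, if there are 7 or fewer responses (ORR) among the first 15 subjects, the study will be stopped".

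Section 12.3 sets the maximum sample size at 25. Its February 2023 update plans ten more patients with a "change from SC to IV administration route, up-titration of the anakinra dose in case of breakthrough CRS or ICANS". For the first 15 patients, Section 2.3.2 reports that "there were no adverse events (AEs) attributed to anakinra".

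**The concern.** The criterion, the counts and the suspension probabilities should describe one rule. The one-death limit of 7 looks like the exact point at which the 80% bound crosses 3%. The two-death limit of 15 does not look like such a point. It coincides with the interim sample size instead, and a suspension probability of 0.93 looks too high for a rule that stops looking at patient 15.

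At stake is whether two attributable deaths among patients 16 to 25 suspend enrolment. With cumulative counting from study start, a team working from the counts would not suspend and a team working from the criterion would. These are the patients who receive the changed route and the up-titration, and the quoted 0.93 describes only the second team's rule.

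**Working it through.** **Inputs** (Section 12.4 unless noted): one-sided 80% exact lower bound; threshold 3%; listed limits 7 (one death) and 15 (two deaths); stated probabilities 0.08 at 1% and 0.93 at 15%; 5,000 simulations; maximum 25 patients (Section 12.3).

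**Step 1: the criterion.** The exact (Clopper-Pearson) lower bound for x deaths in n patients is the 20th percentile of Beta(x, n − x + 1).

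| Deaths | n | Lower bound | Above 3%? |
|---|---|---|---|
| 1 | 7 | 3.14% | yes |
| 1 | 8 | 2.75% | no |
| 2 | 15 | 5.53% | yes |
| 2 | 16 | 5.18% | yes |
| 2 | 25 | 3.31% | yes |
| 2 | 27 | 3.06% | yes |
| 2 | 28 | 2.95% | no |

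The one-death limit of 7 is exactly the criterion's limit. The two-death limit is 27, which the maximum sample size caps at 25. A 90% bound does not explain the listed pair either: its limits are 3 and 17.

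**Step 2: the stated probabilities.** Let L be the last patient at which two deaths trigger. The study is not suspended only if there is no death in the first 7 patients and at most one in the next L − 7:

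P(suspend) = 1 − (1 − p)^7 × P[Bin(L − 7, p) ≤ 1]

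At p = 0.15, (0.85)^7 = 0.3206.

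- L = 15: P[Bin(8, 0.15) ≤ 1] = 0.6572, so P = 1 − 0.3206 × 0.6572 = **0.789**.
- L = 25: P[Bin(18, 0.15) ≤ 1] = 0.2240, so P = 1 − 0.3206 × 0.2240 = **0.928**.

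At p = 0.01, (0.99)^7 = 0.9321.

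- L = 15: 1 − 0.9321 × 0.9973 = **0.070**.
- L = 25: 1 − 0.9321 × 0.9862 = **0.081**.

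| True rate | Counts as listed (L = 15) | Two-death count to 25 | Stated |
|---|---|---|---|
| 1% | 0.070 | 0.081 | 0.08 |
| 3% | 0.210 | 0.273 | – |
| 5% | 0.342 | 0.460 | – |
| 10% | 0.611 | 0.785 | – |
| 15% | 0.789 | 0.928 | 0.93 |

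Applying the bound itself after every patient up to 25 gives the same values as the L = 25 column.

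**Step 3: could simulation error or another reading explain 0.93?** With 5,000 runs the standard error at 0.789 is √(0.789 × 0.211 / 5,000) = 0.0058, so 0.93 is (0.93 − 0.7893) / 0.0058, about 24 standard errors away. Adding a three-death trigger to patient 25 to the listed counts gives only 0.861. Intermediate limits give 0.808 (L = 16), 0.872 (L = 20) and 0.919 (L = 24). The 1% figure does not discriminate by itself: its standard error is 0.0036, and a value rounded to 0.08 could be as low as 0.075, against 0.070.

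**Step 4: rule 2 as a contrast.** Its two-sided 95% upper bound is 73.4% at 7/15 and 78.7% at 8/15, so its count agrees with its 75% criterion. P[Bin(15, 0.4) ≤ 7] = 0.787 (stated about 80%) and P[Bin(15, 0.8) ≤ 7] = 0.0042 (stated about 0.5%). Rule 2 is consistent at 15; rule 1 is not.

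**Step 5: what remains live.** With no attributable death in the first 15 and cumulative counting, the two readings differ only if at least two of patients 16 to 25 have an attributable death. P[Bin(10, p) ≥ 2] is 0.004 at 1%, 0.035 at 3%, 0.086 at 5%, 0.264 at 10% and 0.456 at 15%.

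**The case against.** The strongest reply is that the bound defines the rule and the counts are only sufficient examples. Two deaths within 15 patients do satisfy the bound, and the criterion and both quoted probabilities agree once the bound is applied to all 25. On this reading 0.93 is correct and only the list is short. That is a fair reading, but it does not remove the problem. The counts are presented as the operational form of the rule, the one-death limit sits exactly on the criterion's boundary, and nothing is listed after patient 15. The list would still need completing.

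Second, the practical gap depends on cumulative counting. If counting restarted with the expansion cohort, two deaths among those ten patients would fall within the first 15 and would trigger, as would one death in the first 7. Section 12.4 mentions no restart, so counting from study start is the natural reading, but the condition should be kept in view.

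Third, the contrast of 0.789 with 0.928 is measured from patient 1. The remaining divergence is small at low true rates (0.004 at 1%) and large only at rates that nothing in the documents suggests. That is correct, though 15 patients on the earlier regimen do not exclude such rates on the changed one.

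Fourth, the trigger only pauses enrolment for Steering Committee review. Sections 13.1 and 13.2 add review of serious adverse events as they occur, at least monthly review of the stopping rules, and DSMC, IRB and DSMB oversight. This limits the harm, but it does not tell those bodies which version of the trigger governs.

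**Conclusion.** The point stands. In Section 12.4 the two-death limit of 15 agrees neither with the 80%/3% criterion, which two deaths satisfy at every n up to 27, nor with the stated 0.93, which is 0.789 under the listed counts. The criterion and both quoted probabilities fit a two-death count running to patient 25; the 15% figure is the decisive one. The calculation assumes independent deaths at a constant rate and review after each patient. The consequence for patients 16 to 25 further assumes cumulative counting and no attributable death in the first 15. Because this is a death-based safety trigger and the ten remaining patients receive a modified regimen, the text needs correcting, even though the result of a trigger is a pause and other oversight applies.

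**What to change.** Reconcile the criterion, the counts and the probabilities in Section 12.4. There are two consistent ways, and the choice is the sponsor's.

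- **(a)** State the two-death count through patient 25. This agrees with the criterion and with both quoted probabilities. Relative to the listed counts, the chance of an enrolment pause rises from 0.070 to 0.081 at a true rate of 1% and from 0.210 to 0.273 at 3%. If the criterion is already being applied to all 25 patients, nothing changes.
- **(b)** If a limit of 15 is intended, write it into the criterion, as rule 2 does, and restate the probabilities as about 0.07 and 0.79. This adds no pauses, but the stated probability of suspension at a 15% true rate falls from 0.93 to about 0.79.

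Either is about one line of text. It would also help to state whether the expansion cohort is counted together with the first 15 patients.
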